4.1 Inclusion criteria (as described in WHO COVID 19 core protocol)

1. Adult patients, 18 years and above
2. Confirmed SARS-CoV-2 infection by PCR
3. Admitted to the hospital ward or the ICU
4. Subjects (or legally authorized representative) provide informed consent prior to initiation of the study
5. No anticipated transfer within 72 hours to a non-study hospital

4.2 Exclusion criteria

1. Severe co-morbidity with life expectancy <3 months according to investigators assessment
2. ASAT/ALAT > 5 times the upper limit of normal
3. Acute co-morbidity within 7 days before inclusion such as myocardial infarction
4. Known intolerance and hypersensitivity to any of the components of the available study drug.
5. Pregnancy or breast feeding
6. Any reason why, in the opinion of the investigators, the patient should not participate
7. Participation in a potentially confounding drug or device trial during the course of the study
8. Already receiving any of the study drugs
9. Patients on concomitant medications, which are part of the list of prohibited medications, have to be excluded from the current study (**see point 4.3**).

4.3 Prohibited concomitant medication in relation to Remdesivir

Carbamazepine, phenytoin, rifampin, isoniazid, pyrazinamide, nevirapine, ritonavir, sodium valproate/valproic acid

4.4 Baseline characteristics

According to the CRF a description of the included patients co-morbidity, ongoing treatment and performance status (Frailty score) will be required. Severe disease is defined as patients which need ICU management and mild/moderate disease is defined as people which can be treated at the hospital ward.

A pregnancy test will be performed in all women of childbearing potential. For the purpose of this document, a woman is considered of childbearing potential (WOCBP), i.e. fertile, following menarche and until becoming post-menopausal unless permanently sterile. Permanent sterilization methods include hysterectomy, bilateral salpingectomy and bilateral oophorectomy

5 Study products and study drug regimes

See core protocol (Appendix 1 and SOP-4 to SOP-7b). Note that this protocol currently only includes Remdesivir as study drug.

5.1 Remdesivir

The lyophilized formulation of Remdesivir is a preservative-free, white to off-white or yellow, lyophilized solid containing 100 mg of Remdesivir to be reconstituted with 19 ml sterile water for injection and diluted with IV infusion fluids prior to IV infusion. It is supplied as a sterile product in a single-use, 50 mL, Type 1 clear glass vial. Following reconstitution, each vial contains 5 mg/ ml concentrated Remdesivir solution with sufficient volume to allow withdrawal of 20 ml (100 mg of Remdesivir). In addition to the active ingredient, the lyophilized formulation of Remdesivir contains the following inactive ingredients: water for injection, SBECD (sulfobutylether cyclodextrin), hydrochloric acid, and/or sodium hydroxide. Hydrochloric acid and/or sodium hydroxide are used to adjust the formulation to a final pH of 3.0 to 4.0 following reconstitution.

Remdesivir will be delivered by WHO when available. Remdesivir will be given intravenously with a loading dose of 200 mg at inclusion, day 1. Thereafter the patient will receive a daily intravenous maintenance dose of 100 mg from day 2 to day 10.

The total volume of administration can be 250 mL or 500 mL of Normal Saline. The infusion can be administered over a period of between 30 minutes and 2 hours.

5.2.1 Remdesivir and renal function

Particular attention will be paid to patients included in the Remdesivir arm. Daily blood samples will be taken, including eGFR, electrolytes and urea.

5.2.2 Remdesivir and prohibited concomitant medication

When the patient is randomized to treatment with Remdesivir the following list of medication must not be given concomitantly: Isoniazid, rifampin, pyrazinamide, nevirapine, ritonavir, phenytoin, carbamazepine, sodium valproate/valproic acid

5.3 General information on intervention drugs

No clinical drug-drug interaction studies have been conducted with Remdesivir. Although Remdesivir is a substrate for CYP2C8, CYP2D6, and CYP3A4 in vitro, co-administration with inhibitors of these CYP isoforms is unlikely to markedly increase Remdesivir levels, as its metabolism is likely to be predominantly mediated by hydrolase activity. While hepatocyte donor-dependent induction of mRNA levels of CYP1A2 and CYP2B6 was observed, Remdesivir showed no induction of CYP3A4 mRNA or CYP3A4/5 activity. The nucleoside metabolite GS-441524 and the intermediate metabolite GS-704277 showed no induction of CYP enzymes. Consistently, no potential for induction of enzymes or transporters via PXR or AhR was detected in reporter cell lines. Remdesivir is a substrate for OATP1B1 and P-gp. However, the impact of these transporters on Remdesivir disposition is likely minimized by the parenteral route of administration. Remdesivir is an inhibitor of OATP1B1, OATP1B3, BSEP, MRP4, and NTCP in vitro, but its potential to be the perpetrator of clinically significant drug-drug interactions is limited by its rapid clearance. The major systemic metabolites of Remdesivir, GS-704277 and GS-441524, are not inhibitors of human BSEP, MRP2, MRP4, or NTCP transporters (IC50 > 100 µM). If unanticipated drug-drug interactions are observed, the short-term course of Remdesivir treatment may allow for temporary dose modification of other interacting drugs. The drugs that may influence the metabolism of Remdesivir to a clinically significant level include dexamethasone, haloperidol, carbamazepine, phenytoin, rifampin and phenobarbital.

Information about the administration, preparation, doses, storage and handling, disposition of unused product and the maintenance of inventory logs is provided in the Pharmacy manuals for Remdesivir (SOP-4).

6 Drug discontinuation and patient withdrawal

As described in the core protocol (Appendix 1):

At all times the patient's medical team remains solely responsible for decisions about that patient's care and safety. Hence, study drug administration must be stopped if the team suspects any serious unexpected drug-related reaction that is life-threatening. The study will be stopped in case of occurrence of AEs unknown to date in respect to their nature, severity, and duration that may negatively affect the benefit/risk of the trial.

Patients are free to withdraw from study treatment at any time, but could still remain in the study, with in-hospital outcome reported to the study at death or discharge.

Patients are also free to withdraw from the whole study at any time without any consequence and would continue to be offered the local standard of care (but not be reported on). When patients cannot withdraw from study treatment or the whole study themselves, due to their current health status, an appropriate patient representative can withdraw them on their behalf

7 Study assessments and procedures

The WHO core protocol assesses all-cause-in-hospital-mortality. In addition the following will be assessed for this national add-on protocol (see flow chart).

7.1 Clinical variables

Collecting of daily clinical data will start when the patient is included in the study and be continued until the patient is discharged or dies. The following data will be collected (See, flow-chart for detailed description)

- Regular blood samples
- Respiratory support
- Other organ supportive support therapy (e.g., circulatory, kidney)
- SOFA score at admittance and day 3-5, 7-9
- Blood pressure, heart rate, respiratory rate, oxygen tension and temperature (for patients at hospital ward/not ICU)
- Echocardiography within the first week and after 3 months
- Co-infections
- Antimicrobial treatment in addition to the study drug
- Chest X-ray or CT scan during hospitalization and CT scan after 3 months
- Pulmonary functional test at 3 months
- Rectal swab sample at 3 months

Samples required for clinical management will at all times have priority over samples taken for research tests. Aliquots or samples for research purposes should never compromise the quality or quantity of samples required for medical management. Wherever practical, taking research samples should be timed to coincide with clinical sampling.

7.2 Case report form and patient numbers

There will be two electronic web-based case report forms (eCRFs) for data entering. The core data collection and randomization will be done in the WHO eCRF (see Appendix 1 for details), while national-specific data according to this protocol will be collected in a separate eCRF. The patient study number issued from the WHO eCRF will be registered in the national eCRF for validity.

The local study site will keep a person-identifiable code secured at a separate place, available only for the primary local investigators. The study samples taken at baseline, day 1, day 3-5, day 7-9, thereafter weekly or when discharged from hospital/ICU, will be assigned a corresponding number to that of the patient as well as a number indicating sample order; (Sample taken day 1= sample 1, taken day 3-5= sample 2, taken 7-9 = 3 and so on).

7.3 Risks to participants

7.3.1 Remdesivir

Risks associated with Remdesivir treatment are expected to be hypotension (9), transient elevation in transaminases and transiently increased respiratory rate (personal communication with the manufacture).

7.3.2 General risk considerations

The patients included in this study will be severely ill, possibly in need of organ supportive care, and the implementation of a new drug in this situation may induce unknown effects that may aggravate organ dysfunction. Thus, Remdesivir must be provided under special vigilance. On the other hand patients with COVID-19 infection at ICU will have a high mortality rate and without any

established anti-viral therapy, the potential beneficial effects of this promising anti-viral agent will in our opinion outweigh the potential adverse effects of drugs in this severely ill patient group.

Blood sampling: This represents an insignificant inconvenience for the included patients. Blood samples will be taken at baseline (day 1) and day 3-5, and will constitute a minimal blood loss and no harm for the patients.

7.4 Benefits to participants

7.4.1 Remdesivir

We anticipate that intravenous administration of this drug will be particularly beneficial for patients admitted to ICU.

7.5 Specimens and laboratory analysis

Routine medical biochemistry data will be collected daily at each centre and analyzed by the local laboratory.

Samples for SARS-CoV-2 PCR analyses will be analysed in oropharyngeal specimens at admission and every third day.

In addition, blood study samples will be taken at inclusion of the study (baseline) and at day 4 (3-5) and day 8 (7-9), thereafter weekly and at three months. At each time point it will be taken: (i) EDTA, 12 mL and (ii) Serum 8 mL. Additionally, some study sites will take whole blood EDTA samples (5 mLs) and blood for isolation of peripheral blood mononuclear cells (PBMC; 16 mLs) three times during the study. It might be difficult for all participating centers to collect these samples therefore lack of collection will not be considered as a protocol deviation.

Samples will be processed and centrifuged within 1 hour and stored at -80°C (PBMC in -80 °C or in liquid nitrogen) before analysed collectively at Research Institute of Internal Medicine, and Department of Immunology, Oslo University Hospital. We recognize that -80°C storage is not available at all sites. In this case it will be possible to store the samples temporarily at -20°C for 1 month before transfer to the Research Institute of Internal Medicine and Department of Immunology, Oslo. For preparation of plasma and serum, see also appendix A5.

Strict Biosafety procedures and international regulations will be applied with regard to the collection, storage, transfer and laboratory handling of research samples. Appropriate processing and storage of samples will be carefully reviewed when different hospitals and study sites decide to adhere to the study.

Research Institute of Internal Medicine at Oslo University hospital has extensive experience in analysing relevant markers in a large number of samples using multiplex technology, enzyme immune assays on a robot platform and proteomics.

8 Data management

International data management will be performed by the WHO (see Appendix 1), while national data management will be performed at Oslo University Hospital. Patients' identities will be protected and their information held securely. Only anonymized data will be stored at the web databases, whereas the participant list will be stored separately, secured, at the different local study sites.

It is important that data generated now are not destroyed unnecessarily, since they will be of considerable potential value to future generations faced with similar outbreaks of infectious disease. Electronic data and electronic copies of paper documents will be stored for at least 15 years.

9 Safety monitoring and reporting

The PI is responsible for the detection and documentation of events meeting the criteria and definition of an adverse event (AE) and a serious adverse event (SAE). The sponsor is responsible for assessing whether a SAE is defined as SUSAR as well as for reporting of all SUSARs to the national competent authority. Each patient will be instructed to contact the investigator immediately should they manifest any signs or symptoms they perceive as serious. Safety analyses will include tabulation of the type and frequency of adverse events. Any serious adverse events will be reported with comprehensive narratives. Any value of safety laboratory parameters outside the expected ranges will be identified. The methods for collection of safety data are described below.

9.1 Adverse Events and Serious Adverse Events

9.1.1 Definition of Adverse Event (AE)

AE means any untoward medical occurrence associated with the use of an intervention in humans, whether or not considered intervention related. An AE can therefore be any unfavorable and unintended sign (including an abnormal laboratory finding), symptom, or disease temporally associated with the use of medicinal (investigational) product.

Any medical condition that is present at the time that the subject is screened will be considered as baseline and not reported as an AE. However, if the severity of any pre-existing medical condition increases, it should be recorded as an AE.

Given the nature of severity of the underlying illness, subjects will have many symptoms and abnormalities in vitals and laboratory. All Grade 3 AEs will be captured as AEs in this trial and will be considered as notable events. For Remdesivir, additional information on AE grade 1 or 2 occurring while administration or within the first hour will be reported in the eCRF in a separate form; *Remdesivir, mild adverse reaction (grade 1 & 2)*.

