9.1.2 Definition of Serious Adverse Event (SAE)

An SAE is defined as “An AE or suspected adverse reaction is considered serious if, in the view of either the investigator or the sponsor, it results in any of the following outcomes:

- Death,
- a life-threatening AE,
- prolongation of existing hospitalization,
- a persistent or significant incapacity or substantial disruption of the ability to conduct normal life functions,
- or a congenital anomaly/birth defect.
- important medical events

Important medical events that may not result in death, be life-threatening, or require hospitalization may be considered serious when, based upon appropriate medical judgment, they may jeopardize the patient or subject and may require medical or surgical intervention to prevent one of the outcomes listed in this definition

“Life-threatening” refers to an AE that at occurrence represents an immediate risk of death to a subject. An event that may cause death if it occurs in a more severe form is not considered life-threatening. Similarly, a hospital admission for an elective procedure is not considered a SAE. All SAEs, as with any AE, will be assessed for severity and relationship to study intervention. All SAEs will be recorded on the appropriate SAE CRF. All SAEs will be followed through resolution or stabilization by a licensed study physician.

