9.1.5 Severity of Adverse Events

AEs will be graded according to the following definitions:

- Mild (Grade 1): Events that are usually transient and may require only minimal or no treatment or therapeutic intervention and generally do not interfere with the subject’s usual activities of daily living.
- Moderate (Grade 2): Events that are usually alleviated with additional specific therapeutic intervention. The event interferes with usual activities of daily living, causing discomfort but poses no significant or permanent risk of harm to the research subject.
- Severe (Grade 3): Events interrupt usual activities of daily living, or significantly affects clinical status, or may require intensive therapeutic intervention. Severe events are usually incapacitating.
- Life-threatening (Grade 4): Urgent intervention indicated.

AEs characterized as intermittent require documentation of onset and duration of each episode. The start and stop Duration of each reported AE will be recorded on the appropriate CRF. Changes in the severity of an AE will be documented to allow an assessment of the duration of the event at each level of intensity.

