9.1.7 Time Period and Frequency for Event Assessment and Follow-Up

For this study, all Grade 3 and 4 AEs, Grade 1 and 2 AEs for Remdesivir occurring while administration or within the first hour and all SAEs occurring from the time the informed consent is signed through three months follow-up will be documented, recorded, and reported.

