9.3 Safety Committee

There will be two Data and Safety Monitoring Committees (DSMC), one global and one national. The global is detailed in the core protocol (Appendix 1) while the national DSMC will monitor the safety and evaluate the risk-benefit of the study interventions in the Norwegian patients. The national DSMC will consist of two clinicians and one statistician.

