10.5.3 Safety analyses

Safety endpoints include death through three months, SAEs, discontinuation of study infusions, and severe AEs. These events will be analysed univariately and as a composite endpoint. Time-to-event methods will be used for death and the composite endpoint. Each AE will be counted once for a given participant and graded by severity and relationship to COVID-19 or study intervention. AEs will be coded using the current version of the Medical Dictionary for Regulatory Activities (MedDRA). AEs will be presented by system organ class, duration (in days), start- and stop-date. Adverse events leading to premature discontinuation from the study intervention and serious treatment-emergent AEs should be presented either in a table or a listing.

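### COVID-19 progression counts as an adverse event and is not separated in the SAE, severe-AE and composite safety endpoints, which therefore overlap with efficacy and can hide or dilute drug toxicity

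*Protocol*

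**What the plan says.** Inclusion criterion 2 (section 4.1) is "Confirmed SARS-CoV-2 infection by PCR", so COVID-19 is present at screening in every patient. Section 9.1.1 first sets such conditions aside: "Any medical condition that is present at the time that the subject is screened will be considered as baseline and not reported as an AE". It then reverses this for worsening: "However, if the severity of any pre-existing medical condition increases, it should be recorded as an AE". The next paragraph acknowledges the severity of the underlying illness but does not exempt its progression.

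Section 9.1.5 grades an event as severe when, among other things, it "significantly affects clinical status, or may require intensive therapeutic intervention". Section 9.1.2 makes an event serious if it results in death, is life-threatening, or causes "prolongation of existing hospitalization". Section 9.1.7 collects Grade 3 and 4 events and adds that all "SAEs occurring from the time the informed consent is signed through three months follow-up will be documented, recorded, and reported".

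Section 10.5.3 states: "Safety endpoints include death through three months, SAEs, discontinuation of study infusions, and severe AEs". These are analysed one by one and as a composite. The same section grades each AE by its relationship to COVID-19 or to the study intervention and tabulates AEs by system organ class. Section 9.3 says that "the national DSMC will monitor the safety and evaluate the risk-benefit of the study interventions in the Norwegian patients".

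In section 3, in-hospital death is the primary endpoint, and receipt of mechanical ventilation and of intensive care are secondary endpoints.

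**The concern.** A patient whose COVID-19 worsens to the point of intensive care, ventilation or death has reached an efficacy endpoint. Under sections 9.1.1, 9.1.2 and 9.1.5 that patient will usually also have a Grade 3-4 AE, and often an SAE. The same event then enters both the benefit and the risk side.

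This can mislead in two ways. If remdesivir reduces progression, the fall in progression events offsets toxic events in the SAE and severe-AE totals, and a harmful effect can look neutral or protective. If remdesivir has no effect on progression, the progression events add noise that dilutes a toxicity difference. Both matter for the final safety comparison, and for a national DSMC asked to weigh risk against benefit if it is shown only the totals.

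**Working it through.** **Inputs from the protocol.** Section 10.1 gives 26% in intensive care (70 of 268), a 10-point difference of interest (so 16% on remdesivir) and 406 per arm. Section 10.2.1 gives equal allocation.

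**The plan's own figure.** With unpooled variance, n = (z₀.₉₈₇₅ + z₀.₉₀)² × [p₁(1−p₁) + p₂(1−p₂)] / d² = (2.241 + 1.282)² × (0.26×0.74 + 0.16×0.84) / 0.10² = 12.41 × 0.3268 / 0.01 = 405.6, so 406 per arm. The figure reproduces and is not in dispute.

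**Assumptions, not in the documents.** Every progression case is an SAE. Toxicity is independent of progression. The toxicity rates are chosen for illustration. Then:

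P(any SAE) = 1 − (1 − progression)(1 − toxicity).

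**Step 1: toxic SAEs in 5% on remdesivir, none on standard care.** The break-even toxicity is the progression difference divided by (1 − progression on remdesivir).

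| Progression, standard care vs remdesivir | All-SAE, standard care | All-SAE, remdesivir | Difference | Break-even toxicity |
|---|---|---|---|---|
| 26% vs 16% (planned benefit) | 26.0% | 1 − 0.84×0.95 = 20.2% | −5.8 points | 0.10/0.84 = 11.9% |
| 26% vs 21% (half the benefit) | 26.0% | 1 − 0.79×0.95 = 24.95% | about −1 point | 0.05/0.79 = 6.3% |
| 13% vs 8% (half of the ICU cases already there at entry, same relative effect) | 13.0% | 1 − 0.92×0.95 = 12.6% | −0.4 points | 0.05/0.92 = 5.4% |
| 26% vs 26% (no benefit) | 26.0% | 1 − 0.74×0.95 = 29.7% | +3.7 points | none |

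In the first row the standard error is √[(0.202×0.798 + 0.26×0.74)/406] = 0.0295. The chance of seeing any excess on remdesivir is Φ(−0.058/0.0295), about 2.5%.

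**Step 2: dilution when the drug has no effect on progression.** Take toxicity of 6% vs 1%, that is, the same 5-point excess over an assumed 1% background, tested at a nominal two-sided 5%.

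- Set apart: SE = √[(0.06×0.94 + 0.01×0.99)/406] = 0.0128. Power = Φ(0.05/0.0128 − 1.96), about 97%.
- In the aggregate: standard care 1 − 0.74×0.99 = 26.7%; remdesivir 1 − 0.74×0.94 = 30.4%. The difference is 3.7 points and SE = 0.0317. Power = Φ(0.037/0.0317 − 1.96), about 21%.

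With half the benefit (26% vs 21%), the aggregate becomes 26.7% vs 1 − 0.79×0.94 = 25.7%, and the chance of a significant harm signal is about 1%.

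**Step 3: share of the aggregate that is progression.** If 26% of standard-care patients progress and background severe toxicity is 2%, 5% or 10%, patients who progressed make up 0.26/[1 − 0.74×(1 − background)] of those with any severe event, which is about 95%, 88% or 78%. These shares lean high, because the 26% is a cross-sectional count and may include patients already in intensive care at entry.

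**The case against.** The strongest points on the other side are these.

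- **A reader might infer that the safety endpoints mostly re-count efficacy, or that remdesivir will look nearly 6 points safer.** The documents do not support either as a fact. The 26% is the share of patients in intensive care at one time, not a rate of worsening after randomisation. Patients may enter from the ICU, and that status is then baseline. Section 9.1.2 does not list ICU transfer as a criterion, and seriousness rests on the investigator's or sponsor's view. This stands, and it is why a range is given.
- **A reader might infer that the composite always favours the drug.** It need not. Discontinuation of study infusions is one of its components and can occur only on remdesivir, which pushes the composite the other way. No calculation above includes it. This stands; it also means the composite is not a clean measure of toxicity.
- **Toxicity is visible elsewhere.** Section 10.5.3 has relationship grading, organ-class tables and separate analyses of each component. Section 9 has SAE narratives and out-of-range laboratory values. Section 3 has kidney and myocardial endpoints. Infusion-time Grade 1-2 reactions are collected separately. Section 9.3 does not say which tables the national DSMC will see. These soften the problem. They do not define or split the stated endpoints, and the SAE and severe-AE totals each already contain progression. The grading is made open label, and section 9.1.6 allows a temporal relationship alone to make an event related.
- **Excluding progression could remove real harm.** Section 7.3.1 names a transiently increased respiratory rate as an expected risk, and section 7.3.2 warns that organ dysfunction may be aggravated. Section 9.1.8 has sites group signs into one diagnosis, so the recorded term may already carry an unblinded judgement. This stands against making the reduced row the main one. It does not stand against showing both.
- **This is detail for the analysis plan.** The SAP is not shown and may already split these events. But the protocol itself fixes both the AE definition and the safety endpoints, so the point is confined to those two sections as written.

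**Conclusion.** The point holds, in a bounded form. Sections 9.1.1 and 10.5.3 together let COVID-19 progression into the SAE, severe-AE and composite comparisons without separating it, so these endpoints overlap with death, intensive care and ventilation as efficacy outcomes.

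Under the assumptions stated, a true 5-point toxicity excess appears as anything from −5.8 to +3.7 points in the all-SAE comparison, depending on how much progression occurs after entry and how much the drug prevents. It is fully hidden in three of the four scenarios. In the fourth, with no benefit, it is diluted; there the comparable 6% vs 1% case drops from about 97% to about 21% power. The direction for the composite cannot be stated, because infusion discontinuation acts against remdesivir. The plan should be changed on this point, but organ-specific toxicity still has other routes to show itself.

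**What to change.** Leave the recording rule in section 9.1.1 and the expedited reporting rules as they are. In section 10.5.3:

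- Pre-specify COVID-19 progression events by objective event type: death from COVID-19, ICU admission and mechanical ventilation. Have them flagged without sight of the arm. Cause of death needs judgement, so the arm-blind step matters most there.
- Report SAEs, severe AEs and the composite in two rows, all-cause and excluding the flagged events, side by side, with neither replacing the other.
- Give the national DSMC both rows.

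The cost is protocol or SAP wording, one flag and one extra table. The downside is that respiratory worsening caused by the drug may be absent from the second row; it stays in the all-cause row.
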